#### **10.4 Informed consent**

The Principal Investigator(s) at each centre will:

- Ensure that each subject is given full and adequate oral and written information about the nature, purpose, possible risk and benefit of the study
- Ensure that each subject is notified that they are free to discontinue from the study at any time
- Ensure that each subject is given the opportunity to ask questions and allowed time to consider the information provided
- Ensure that each subject provides signed and dated informed consent before conducting any procedure specifically for the study
- Ensure that the original, signed ICF(s) is/are stored in the Investigator's Study File
- Ensure that a copy of the signed ICF is given to the subject
- Ensure that any incentives for subjects who participate in the study as well as any provisions for subjects harmed as a consequence of study participation are described in the ICF that is approved by an EC.

#### **10.5 Changes to the protocol and informed consent form**

Study procedures will not be changed without the mutual agreement of the International Coordinating Investigator and AstraZeneca or designee.

If there are any changes to the study protocol, then these changes will be documented in a new version of the study protocol.

If applicable, the new version of the protocol is to be approved by the relevant EC and the national regulatory authority before implementation. Local requirements are to be followed for revised protocols.

AstraZeneca or designee will distribute any subsequent amendments and new versions of the protocol to each Principal Investigator(s). For distribution to ECs, see Section 10.3.

If a protocol amendment requires a change to a centre's ICF, AstraZeneca or designee and the centre's EC are to approve the revised ICF before the revised form is used.

If local regulations require, any administrative change will be communicated to or approved by each EC.

## **10.6 Audits and inspections**

Authorised representatives of AstraZeneca, a regulatory authority, or an EC may perform audits or inspections at the centre, including source data verification. The purpose of an audit or inspection is to systematically and independently examine all study-related activities and documents to determine whether these activities were conducted and data were recorded, analysed, and accurately reported according to the protocol, GCP, guidelines of the ICH, and any applicable regulatory requirements. The Investigator will contact AstraZeneca or designee immediately if contacted by a regulatory agency about an inspection at the centre.

[figure not shown]

## LIST OF ABBREVIATIONS

Abbreviation or special term	Explanation
████	████████████████
AE	Adverse event
AESI	Adverse event of special interest
ALT	Alanine transaminase
AST	Aspartate transaminase
████	████████████████
BDR	Blind delivery review
BMI	Body mass index
██	████████████████████
██	████████████████████████████
████	████████████████████
CI	Confidence interval
COVID-19	Coronavirus disease 2019
CRO	Clinical research organisation
CSR	Clinical Study Report
CV-EAC	Cardiovascular Event Adjudication Committee
dsDNA	Double-stranded deoxyribonucleic acid
DSMB	Data and Safety Monitoring Board
ECG	Electrocardiogram
eCRF	Electronic Case Report Form
EDV	Early Discontinuation Visit
████████	████████████████████
GGT	gamma glutamyl transferase
IFN	Interferon
IP	Investigational product
IV	Intravenous
IXRS	Interactive Voice/Web Response System
LOCF	Last observation carried forward
LTE	Long-term extension

Abbreviation or special term	Explanation
MACE	Major adverse cardiovascular events
█	█
MedDRA	Medical Dictionary for Regulatory Activities
█	█
OCS	Oral corticosteroids
█	█
PGA	Physician's Global Assessment
█	█
█	█
Q	Question
Q-Q	Quartile-quartile
Q4W	Every 4 weeks
SAE	Serious adverse event
SD	Standard deviation
█	█
TELVC	Treatment-emergent laboratory/vital signs changes
SELENA	Safety of Estrogens in Lupus Erythematosus National Assessment
█	█
SLE	Systemic lupus erythematosus
SLEDAI-2K	Systemic Lupus Erythematosus Disease Activity Index 2000
SOC	Standard of care
ULN	Upper limit of normal
█	█
WHO-DD	World Health Organization Drug Dictionary
WOCF	Worst observation carried forward
█	█

## AMENDMENT HISTORY

Date	Brief description of change
29 Jul 2019 (v2.0)	

• Clarified the definition of treatment groups and added a descriptive figure.

• Added the Full Analysis Set – LTE Study analysis set for use in the LTE only summaries.

• Removed reference to treatment-emergent Adverse Events (AEs) and added definitions for the categories: AEs during treatment, follow-up and during treatment and follow-up. Added analyses by categories for select AE summaries.

• Expanded the definition for duration of exposure to account for specific treatment groups.

 
█ [REDACTED]
 
█ [REDACTED]
 
█ [REDACTED]
 

• Added to the changes from protocol specified analyses to identify clarification for the treatment groups and analysis sets.

Date	Brief description of change
15 Apr 2020 (v3.0)	

• Updates which are editorial in nature and do not impact the analyses are not listed.

• Section 3.1: Added clarification regarding the analysis of data from subjects who did not participate in the LTE in non-visit-based analyses.

• Section 3.1.1: Updated the definition of “Year 1”.

• Section 4.1.1: Updated the sentence regarding the exclusion of subject [REDACTED] from analyses.

• Section 0: Updated rules in case of multiple readings recorded within a single visit window (unscheduled vs. scheduled visits; antinuclear antibody titres; week 52 data from Phase 3 feeder studies which were imputed using LOCF).

• Section 4.1.4: Clarified the use of LOCF.

• Section 4.1.4: Clarified the calculation of scores.

17 Mar 2021 (v4.0)	

• Section 4.1.1: Added the paragraph regarding the exclusion of site [REDACTED] from analyses.

---

Date	Brief description of change
14 Apr 2022 (v5.0)	

• Updates which are editorial in nature and do not impact the analyses are not listed.

• Added definitions and analyses of COVID-19 events and impact of the COVID-19 pandemic on the analysis. Sections 2.2, 3.1.1, 3.3.5, 4.2.1.1, 4.2.3.1.

• Section 4.1.1: Added the paragraph regarding the exclusion of site [REDACTED] from analyses.

• Section 3.2.3.3: Added details regarding faulty reagents issue.

• Section 4.1.1, 4.2.1.1: Sensitivity analyses including ALL patients (including the patients excluded), add subjects to be excluded.

• Safety: 90% CI replaced by 95% CI

• Addition of safety analysis set (section 2.1.3) and safety analysis set – LTE study (section 2.1.4)

• Section 3.1.6: Cholesterol to be considered only if the subject fasted for at least 8 hours prior to the assessment.

• [REDACTED]

• [REDACTED]

• [REDACTED]

• [REDACTED]

• Section 3.3.3: Updated definition of concomitant medication – include medication up to end of study/participation).

• Section 3.3.4: Added definition of infusion of IP.

• Section 4.1.2: Update of visit windows to cover safety follow-up after week 208.

• [REDACTED]

• Section 4.2.3.1: Updated wording regarding completion of the phase 3 feeder studies.

• Section 5: Add details regarding the interim analysis.

---

## 1. STUDY DETAILS

### 1.1 Study objectives

[figure not shown]
#### 1.1.1 Primary objective

Primary Objective:	Outcome Measure:
To characterise the long-term safety and tolerability of intravenous (IV) anifrolumab	Rates of adverse events of special interest (AESIs) and serious adverse events (SAEs)

#### 1.1.2 Secondary objectives (not applicable)

#### 1.1.3 Safety objective

See Section [1.1.1](#) Primary objective.

## 1.2 Study design

This is a Phase 3, multicentre, multinational, randomised, double-blind, placebo-controlled extension study characterising the long-term safety and tolerability of an IV treatment regimen of anifrolumab (300 mg) versus placebo in subjects with moderately to severely active systemic lupus erythematosus (SLE) who completed a Phase 3 study (D3461C00004 or D3461C00005) through the 52-week double-blind treatment period.

Approximately 575 subjects from Studies D3461C00004 or D3461C00005 (also referred to as the feeder studies) who were previously treated with anifrolumab (150 or 300 mg) or placebo for 52 weeks while receiving standard of care (SOC) treatment and who are willing to continue treatment may participate in the long-term extension (LTE) study if all eligibility criteria are met. Subjects will receive either a fixed IV dose of 300 mg anifrolumab every 4 weeks (Q4W) for up to 39 doses (LTE Week 0 to LTE Week 152) or placebo. Investigational product (IP) will be administered as an IV infusion via an infusion pump over a minimum of 30 minutes, Q4W.

In order to ensure that subjects with active SLE who enter the LTE will have adequate treatment of their disease in this 3-year blinded, placebo-controlled extension study, Investigators will be allowed to change the background SOC treatment for SLE during the course of the study. This LTE protocol allows for adding a new oral immunosuppressant or changing background immunosuppressants, as well as for flexible oral corticosteroids (OCS) use, so that subjects may achieve adequate control of their disease on study. However, it is recommended that subjects receive the lowest possible corticosteroid dose.

In the LTE study, treatment assignment will follow an Interactive Voice/Web Response System (IXRS) algorithm as follows:

- Subjects previously treated with anifrolumab 300 mg IV will stay on blinded treatment
- Subjects previously treated with anifrolumab 150 mg will switch to blinded anifrolumab 300 mg
- Subjects previously randomised to placebo will be re-randomised 1:1 to blinded anifrolumab 300 mg or placebo

Therefore, in the LTE study subjects will receive double-blind treatment with either anifrolumab 300 mg or placebo in an approximate ratio of 4:1.

Although the study will initially be completely double-blind (ie, blind for subjects, Investigators/site staff, and Sponsor/designated clinical research organisation [CRO]), at the conclusion of the Phase 3 Studies D3461C00004 or D3461C00005 treatment allocation for all subjects who were previously on active treatment will become known to the Sponsor staff and/or designated CRO. The blind will be maintained for the Investigator and investigational site staff, for select roles at the CRO, and for the subjects. Further details are described in a separate unblinding plan.

In general, the first dose of study drug in the LTE study (LTE Day 1/Visit 1/Week 0) should occur on the same day as the final study visit of the prior study (ie, Week 52); however, special circumstances may warrant a delay in subject randomisation of up to 30 days following the final visit of the prior study (ie, Week 52). Administration of study drug in the LTE study should not occur until all LTE Day 1/Visit 1/Week 0 evaluations are completed.

This LTE study includes:

- **Treatment Period:** A 156-week treatment period with investigational product administered Q4W from LTE Week 0 to LTE Week 152 for a total of 39 doses. During the treatment period, visits will be scheduled for each Q4W administration.
- **At LTE Week 156 (or after the last dose of investigational product)** subjects will continue in the study for another 8 weeks to complete a 12-week safety follow up after the last dose of investigational product (last dose of investigational product will be given at LTE Week 152).

The total study duration will be up to approximately 164 weeks (including a 12-week Follow up Period after administration of the final dose).

Once subjects have completed Studies D3461C00004 or D3461C00005 (through Week 52), signed the informed consent form, and met all study eligibility criteria, they may be included in the LTE study.

In the event a site has not obtained the required approval (e.g., regulatory authority, local ethics committee) by the time a subject is eligible to be randomised in the LTE study, the site may be allowed the time to obtain the approval(s).

If due to regulatory delays or other exceptional circumstances it is likely that LTE Day 1/Visit 1/Week 0 will occur greater than 30 days after the final visit of the prior study, the PRA Medical Monitor must be contacted to confirm that the subject will be permitted to be randomised. The rationale for the delayed start, date of last dose of study drug, and subject compliance in the prior study will be reviewed to determine whether the subject will be permitted to be randomised. In addition, all Day 1/Visit 1/Week 0 visit procedures must be performed.

If dosing occurs on the same day of the final visit of the prior study, it should occur after all LTE Day 1/Visit 1/Week 0 assessments have been completed, the Investigator has determined that the subject can continue dosing, and the subject has been re-randomised.

Interim analyses may be performed based on regulatory or other requirements.

### **1.3 Number of subjects**

No formal comparisons are planned in this study; point estimates and confidence intervals (CIs) will be presented for each treatment group separately. The sample size is not based on statistical considerations, but is defined as all subjects who completed the treatment period in

the Phase 3 feeder Studies D3461C00004 or D3461C00005 (through Week 52) and met all study eligibility criteria. Assuming annual dropout rates of 30%, 30%, and 20% following placebo, anifrolumab 150 mg, and anifrolumab 300 mg, and that 90% of the subjects completing studies D3461C00004 or D3461C00005 enter the LTE, follow-up times of approximately 893, 517, and 1343 subject years for the “Randomised Anifrolumab 300 mg,” “Randomised Placebo,” and “All Anifrolumab” treatment groups are expected. Given this exposure, the 95% CIs for an AESI for which the observed incidence rate is 10 events in 1000 subject years will be 5.21 to 19.21 for “Randomised Anifrolumab 300 mg,” and 4.24 to 23.57 for “Randomised Placebo.” For an AESI for which the observed incidence rate is 1 event in 1000 subject years, the 95% CI will be 0.18 to 5.42 for “All Anifrolumab” (0.13 to 7.95 for “Randomised Anifrolumab 300 mg”), and 0.07 to 15.25 for “Randomised Placebo,” using the Rothman-Greenland Method ([Rothman and Greenland, 1998](#)).

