### 1.2 Rationale for study design, doses and control groups

This is a Phase 3, multicentre, multinational, randomised, double-blind, placebo-controlled, long-term extension (LTE) study to characterise the long-term safety and tolerability of an intravenous (IV) treatment regimen of anifrolumab (300 mg) versus placebo in adult subjects

who completed a Phase 3 study (D3461C00004 or D3461C00005) through the 52-week double-blind treatment period.

The LTE will allow subjects to continue with treatment for an extended period of up to 3 years. Subjects who received anifrolumab (150 or 300 mg) in the Phase 3 Pivotal studies will receive anifrolumab (300 mg) and subjects who received placebo in the Phase 3 Pivotal studies will be randomised to receive anifrolumab (300 mg) or placebo in a 1:1 ratio. The expected ratio of subjects receiving anifrolumab (300 mg) vs placebo in the LTE study will be approximately 4:1. Subjects randomised to placebo in the LTE study serve as comparators to support interpretability of the data collected for subjects randomised to anifrolumab. Subjects who were receiving anifrolumab 150 mg in the Phase 3 Pivotal study will switch to 300 mg in the LTE to provide long-term safety data on the higher study dose. This study allows for the addition of new oral immunosuppressants or changing doses of background immunosuppressants, as well as for flexible oral corticosteroids (OCS) use in order for subjects to achieve adequate control of their disease throughout the study.

Although the study will initially be completely double-blind, (ie, blind for subjects, Investigators/site staff, and Sponsor/designated clinical research organisation [CRO]), at the conclusion of the Phase 3 Studies D3461C00004 or D3461C00005 treatment allocation for most subjects will become known to some Sponsor staff and/or designated CRO. The blind will be maintained for the Investigator, investigational site staff, and for the subjects.

A treatment period of 156 weeks is an appropriate study duration to characterise the investigational product's long-term safety profile.

The primary outcome measure is the assessment of adverse events of special interest (AESIs), and serious adverse events (SAEs) to characterise safety profile.

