**Figure 1 Primary: Combined treatment groups Randomised Anifrolumab 300 mg and Randomised Placebo (main comparison)**

**Figure 2 Supportive: Combined treatment groups Placebo Feeder + Placebo LTE and All Anifrolumab**

**Figure 3 Additional Supportive: Combined treatment groups Placebo Feeder + Anifrolumab 300 mg LTE and Anifrolumab 150 mg Feeder + Anifrolumab 300 mg LTE**

[figure not shown]

Additional summaries for data collected during the LTE study only will be presented according to the following supportive LTE treatment groups:

- **Randomised Anifrolumab 300 mg:** As described above but using data collected during the LTE study only, ie, reduced to subjects enrolled to the LTE study.

- **Placebo Feeder + Placebo LTE:** As described above but using data collected during the LTE study only, ie, reduced to subjects enrolled to the LTE study.
- **Placebo Feeder + Anifrolumab 300 mg LTE:** Subjects randomised to placebo in studies D3461C00004 or D3461C00005 and then re-randomised to anifrolumab 300 mg in LTE using data from switch to end of LTE.
- **Anifrolumab 150 mg Feeder + Anifrolumab 300 mg LTE:** Subjects randomised to anifrolumab 150 mg in Study D3461C00005 and then switched to anifrolumab 300 mg in LTE using data from switch to end of LTE.

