### **4.2.1 Analysis of the primary variables (safety variables)**

If not stated otherwise, safety variables will be summarised by combined treatment group for the full analysis set.

The primary assessment will be the comparison between the treatment groups “Randomised Anifrolumab 300 mg” and “Randomised Placebo”. The “All Anifrolumab” treatment group will be used to assess rare events.

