The event rate per 100 subject years including 95% CIs will be summarised for the following categories. Summaries of AESIs will be presented by AESI category (non-opportunistic serious infections, opportunistic infections, anaphylaxis, malignancy, herpes zoster, tuberculosis, influenza, vasculitis [non SLE], and major acute cardiovascular events) and preferred term. Summaries for SAEs will be presented by MedDRA system organ class and preferred term.

- Any AESI
- Any AESI by time interval for the first onset of event – alternative event rates
- Any AE leading to discontinuation of IP by time interval for the first onset of event – alternative event rates (combined feeder & LTE study, by preferred term)
- Any AESI – alternative event rates
- Any SAE (including events with outcome = death) (during treatment and during follow-up separately. No event rate for during follow-up will be presented)
- Any SAE (including events with outcome = death) by time interval for the first onset of event – alternative event rates

The event rate per 100 subject years will be summarised by MedDRA system organ class and preferred term for the following AE categories.

- Any AE (during treatment and during follow-up separately. No event rate for during follow-up will be presented)
- Any AE by descending preferred term (during treatment, and during the LTE treatment)
- Any AE with outcome = death
- Any SAE by descending preferred term (including events with outcome = death) (during treatment, and during the LTE treatment)
- Any AE leading to discontinuation of investigational product
- Any AE by relationship to investigational product (yes, no) (multiple occurrences of an AE in 1 subjects will only be counted once as related if at least one AE is related and as not related if all occurrences are not related)
- Any AE by maximum intensity (mild, moderate, severe) (i.e., multiple occurrences of an AE in 1 subjects will only be counted once with the maximum intensity in this AE)
- Any other significant AE

The alternative event rate per 100 subject years will be summarised by MedDRA preferred term for the following AE categories.

- Any COVID-19 related AE (for the LTE Study only, only subjects remaining in the study on 11-Mar-2020 will be included)
- Any SAE prior to the COVID-19 pandemic (for the LTE Study only)
- Any SAE during the COVID-19 pandemic (for the LTE Study only, only subjects remaining in the study on 11-Mar-2020 will be included)

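### The anifrolumab versus placebo comparison named as the primary safety assessment has no estimate or interval, and the per-group intervals are a poor substitute

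*SAP*

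**What the plan says.** SAP 1.3 states that "No formal comparisons are planned in this study" and that "point estimates and confidence intervals (CIs) will be presented for each treatment group separately". The protocol synopsis and Protocol 8.2 say the same.

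SAP 4.2.1 states: "The primary assessment will be the comparison between the treatment groups" Randomised Anifrolumab 300 mg and Randomised Placebo. The caption of SAP Figure 1 describes the pair as "Randomised Anifrolumab 300 mg and Randomised Placebo (main comparison", and Protocol 8.5.1 makes these the main groups for the primary objective. Protocol 1.2 explains that subjects on placebo in the extension "serve as comparators to support interpretability of the data collected for subjects randomised to anifrolumab".

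For AESIs and SAEs, SAP 4.2.1.1 states: "The event rate per 100 subject years including 95% CIs will be summarised for the following categories". It adds alternative event rates (time at risk to first event), rates by study-year interval, and a Kaplan-Meier plot for each AESI category. All of these are within-group summaries. The visible safety text plans no contrast between the two groups, and SAP section 6 (changes from protocol) does not mention the point.

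**The concern.** The plan names a comparison as primary but does not say what quantity compares the groups or how precisely it will be known. A reader of the final tables will have two rates, each with its own 95% CI.

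Two separate 95% intervals do not make a 95% statement about the difference between the rates. Their overlap is a much stricter criterion than an interval for the difference or ratio, so relying on it leans towards seeing no difference. In a safety study, a missed real increase is the costly error. Part of the placebo group stays on blinded placebo for up to three further years so that this contrast can be made, so the plan should say how it will be quantified.

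**Working it through.** **Inputs.** SAP 1.3 gives "follow-up times of approximately 893, 517, and 1343 subject years" for Randomised Anifrolumab 300 mg, Randomised Placebo and All Anifrolumab. The interval method is exact Poisson at 95% (SAP 4.1.3 and 4.2.1.1).

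**Reproducing the plan's figures.** At 10 per 1000 subject-years the expected counts are 8.93 and 5.17.
- SAP 1.3: rate × exp(±1.96 × √(1/events − 1/subject-years)) gives 5.21–19.21 for anifrolumab and 4.24–23.58 for placebo. The SAP prints 5.21–19.21 and 4.24–23.57.
- SAP 4.1.3: chi-square (exact Poisson) limits give 4.56–19.03 and 3.32–23.03, as printed. The formula displayed there is a log-normal one, but the quoted figures come from the exact method, so the exact method is used below.

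**The missing interval in the SAP's own scenario.** With 10 per 1000 in both groups, the rate ratio is 1.00 and SE(log ratio) = √(1/8.93 + 1/5.17) = 0.553. The 95% CI is exp(±1.96 × 0.553) = 0.34 to 2.95.

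**Where separate and direct intervals disagree.** Take 5 placebo events: 5/517 = 9.67 per 1000, exact CI 3.14–22.57. The exact ratio interval applies Clopper-Pearson limits for p to the anifrolumab share of all events and converts them by ratio = p/(1 − p) × 517/893. For 24 of 29 events, p runs from 0.64225 to 0.94154, which gives 1.04 to 9.33.

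| Anifrolumab events | Rate per 1000 (exact CI) | Overlaps placebo CI? | Rate ratio (exact CI) |
|---|---|---|---|
| 23 | 25.8 (16.3–38.6) | yes | 2.66 (0.99–8.97) |
| 24 | 26.9 (17.2–40.0) | yes | 2.78 (1.04–9.33) |
| 26 | 29.1 (19.0–42.7) | yes | 3.01 (1.14–10.04) |
| 29 | 32.5 (21.7–46.6) | yes | 3.36 (1.29–11.11) |
| 30 | 33.6 (22.7–48.0) | no | 3.47 (1.33–11.47) |

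The two disagree from 24 to 29 events; 24 is the threshold case.

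**How often this matters.** The table gives the chance of showing a difference by each criterion, with independent Poisson counts on 893 and 517 subject-years. The true ratios, and placebo rates other than 10 per 1000, are assumptions.

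| Placebo rate per 1000 | True ratio | Non-overlap | Exact ratio CI excludes 1 |
|---|---|---|---|
| 10 | 1 | 0.2% | 2.5% |
| 10 | 2 | 6% | 23% |
| 10 | 3 | 36% | 67% |
| 20 | 2 | 20% | 48% |
| 50 | 2 | 68% | 90% |

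At the SAP's other scenario, 1 per 1000, the two criteria disagree in only about 0.1% of trials even for a true tripling.

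**Choice of interval.** For 24 versus 5 events the crude difference is 26.9 − 9.7 = 17.2 per 1000. Its Wald SE is 1000 × √(24/893² + 5/517²) = 6.99, so the CI is 3.5 to 30.9. For 23 versus 5 the Wald CI is 2.6 to 29.6, which excludes zero, while the exact ratio interval (0.99–8.97) includes 1. A Wald interval is therefore not dependable at these counts.

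**The case against.** The strongest reply is that the absence of a contrast is deliberate. The sole objective is to characterise long-term safety, the outcome measure is rates, and both documents decline formal comparisons. The comparison in SAP 4.2.1 can then be read as side-by-side description. This stands in part: the lack of a hypothesis test is not an error, and no planned rate or interval becomes wrong. But a difference or ratio with a CI, labelled descriptive, is not a test, and SAP 4.2.1 already commits to comparing.

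A reader might infer that the plan makes overlap of intervals the criterion, or hides the comparison. The documents do not support that. Neither document prescribes overlap. The planned rates, exposure totals, interval-specific rates and Kaplan-Meier plots would let a reader work out a crude ratio.

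That crude ratio would need care, however. Under SAP 2.1.6, placebo subjects re-randomised to anifrolumab leave Randomised Placebo at the switch, so placebo time is weighted towards Year 1. If risk changes over time, a pooled contrast mixes treatment with duration. The calculations above are unstratified and carry the same limitation.

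Two practical objections also stand. By preferred term the contrasts would be sparse, numerous and prone to false signals. With about five placebo events spread over five study-year intervals, some strata will probably be empty, so the method must cope with zeros.

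**Conclusion.** The point holds as a cheap improvement: the comparison named as primary has no estimate and no interval, and the per-group intervals are a weak stand-in. At an assumed 10 per 1000 on placebo, non-overlap would show a true tripling in 36% of trials, against 67% for a direct interval. For very rare AESIs the gain is negligible.

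It would go too far to say that readers must judge by overlap or that the plan gives wrong results.

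The figures rest on the SAP's expected follow-up, which cannot be rebuilt because feeder-study arm sizes are not given. They also assume constant rates, independent Poisson counts and the rates and ratios shown. Redacted text could contain a comparative analysis, but the adverse-event analysis section appears intact.

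**What to change.** For any SAE, any AESI and each AESI category, but not by preferred term, add one rate difference or rate ratio with a 95% CI for Randomised Anifrolumab 300 mg versus Randomised Placebo.

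- Base it on the alternative event rate (time at risk) already defined in SAP 3.1.1.
- Stratify by the study-year intervals in SAP 3.1.1 and, where counts allow, by feeder study, which Protocol 3.4 uses to stratify randomisation.
- Use Mantel-Haenszel-type weights with an exact or score-type interval that tolerates zero cells, not a Wald interval.
- Label it descriptive and unadjusted for multiplicity, with no hypothesis test, and reword SAP 1.3 and 4.2.1 so that they agree.

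The rates by study-year interval are already planned, so the cost is modest programming, mainly for the stratification, and some extra table entries. With nine AESI categories plus any AESI and any SAE, that is 11 intervals. Some will be wide, and a footnote should warn that they are unadjusted.
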